#### 6.2 PHOTOGRAPHS

- Photographs will be taken with de-indentified periwound stickers; the patient number, date, dressing change number and protocol reference number should be entered. The label should be placed so that it lies flat along one of the borders of the incision site and not covering any part of the incision.
- When taking photographs ensure that the label details and wound are clearly visible and that the wound takes up the majority of the photograph area.

# 7 ADVERSE EVENTS

This evaluation is being conducted on a product which is available commercially and which is being used within its licensed indications, according to its instructed method of use. In addition, the patient is being treated according to normal practice and no invasive or non-routine assessments are being taken. Therefore, only adverse events that are related to the evaluation product are to be reported.

Adverse Event Reporting. Throughout the Study, Sponsor Investigator agrees to procure that any Device Deficiency ("**DD**"), Adverse Device Effect ("**ADE**") and Serious Adverse Device Effect ("**SADE**") (all as further described in Exhibit A) that are considered as being related to the use of the medical device Avance Solo is reported in accordance with applicable local and/or regulatory requirements and, in addition thereto, be communicated in connection to the regular reports as described in clause **Error! Reference source not found.** Institution shall ensure that it and the

Sponsor-Investigator respond promptly to all requests for follow-up information from Molnlycke. Institution shall ensure that it and Sponsor-Investigator inform IRB of any adverse event, in accordance with the policies and procedures of IRB."

A product related adverse event is any untoward medical occurrence which was possibly, probably or highly probably caused by the use of the evaluation product. If a product related adverse event occurs the evaluation clinician should complete the Clinical Evaluation Adverse Event Form and fax it to the Mölnlycke.

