#### 2 EVALUATION DESIGN

# 2.1 EVALUATION DESIGN

Open label, two armed, prospective, single center, quality equivalency assessment.

Immediate post operative application of Avance® Solo Negative pressure wound therapy on "high risk" closed surgical incisions. Versus the hospital best clinical practice dressing HAAMPOD. (Please note there is no prospective clinical data driven data, the hospital purchasing department develops and indicates the brand based upon cost).

The patient will be undergoing:

- Foot and ankle surgery
- Vascular groin incision, vascular axillary incisions
- Long leg vein harvest incision
- Closed forefoot and major amputation surgery
- Possibly: breast augmentation and reduction surgery

\*Note: The surgical indication is chosen based upon previously published data of high risk incisions. (It is beyond the scope of a protocol to educate the IRB in regards to the full definitions of high risk surgical inicisions)

Patients will participate in the study for 4 applications or up to 2 weeks treatment, whichever comes first. During this time clinicians will be asked to complete questions pertaining to the incision and to the performance and overall acceptability of Avance®Solo or the HAAMPOD.

Throughout the evaluation patients will be treated according to the product instructions for use for either product.

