# 3 EVALUATION PRODUCT(S)

# 3.1 DESCRIPTION OF EVALUATION PRODUCT(S)

Avance® Solo will include the collective description for a complete device capable of delivering negative pressure to the incision site and managing exudate generated by the incision. It comprises:

"This investigation pertains to Avance®Solo, a single use battery powered negative pressure system, with Mölnlycke as the legal manufacturer with its headquarter located in Gothenburg, Sweden. Avance®Solo consists of different products that are FDA compliant, which together form a system for wound management via the application of negative pressure (Figure 2). Avance®Solo maintains negative pressure nominally at -125 mmHg on low and moderately exuding wounds. The pump is pocket sized and can be carried in a pocket or attached to a belt with a belt clip that is assembled with the pump. To maintain the pressure, there is a recycling sound. To reduce the sound of cycling, a night case can be used to facilitate comfort during sleep."

A proprietary Controlled Fluid Management (CFM) technology, the Avance® Solo single use negative pressure system shares fluid management between an absorptive multi-layered dressing and a 50ml canister, reducing the potential for dressing saturation. This technology is theoretically designed to reduce the potential loss of therapy arising from dressing saturation.

 The addition of a canister to the absorptive dressing ensure the dressing does not become overwhelmed with draining and therapy will continue to be delivered regardless of dressing saturation

- Sharing fluid management between an absorptive dressing and canister can reduce the frequency of dressing changes
- Avance® Solo NPWT system continues to deliver negative pressure to the wound site, even with low to moderate amounts of fluid saturation in the dressing
- Avance® Solo features both audible and visual alarms so therapy can be restored in an efficient timely manner
- Avance Solo Border dressings Safetac® adhesive has been proven to minimise trauma to wound site and surrounding skin upon dressing removal
- -125mmHg continuous negative pressure

The pump is a controllable vacuum pump apparatus, which can be left to operate automatically, delivering continuous negative pressure (nominally -125mmHg) to the incision site. The pump's lifetime is 14 days and is powered with 2 lithium batteries specific to the pump. Batteries shall be replaced once pump alarms for Low battery or after 7 days.

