# 3.3 RECONCILIATION

All evaluation products, which have not been used by the end of the evaluation, must be returned to Molnlycke. The clinician will maintain an inventory, which will include details of receipt, use and return of all evaluation products (Appendix 1). The control product will be managed by the Mount Sinai West operating room product acquisition supply system.

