# At end of evaluation

- Reason for discontinuation (end of evaluation, wound closed, treatment interrupted for more than 3 days, Wound progressed sufficiently to warrant a change in treatment, patient withdrawn)
- Reason for patient withdrawal (product related adverse event, lack of response, poor compliance, patients own request, other)
- Overall acceptability of Avance®Solo to clinicians for indicated use (yes/no)
- Whether the clinicians were sufficiently satisfied with the following properties of the product overall in terms of:
- Exudate management
- Conformability
- Number of dressing changes, strips, pumps, canisters and batteries used
- Barrier to infection
- Condition of surrounding skin
- General (Ease of use, Dressing retention, durability, patient comfort & convenience)

- Pain on application of dressing (0-10 SCALE)
- Pain on removal of dressing (0-10 SCALE)
- Overall performance of dressing (1-5)
- Freedom from re-admission
- The use of post operative antibiotics
- The duration of post operative antibiotics if used

Comparison of Avance®Solo with HAAMPOD, whether the clinicians were satisfied with Avance®Solo compared to HAAMPOD:

- Exudate management
- Conformability
- Number of dressing changes
- Barrier to infection
- Condition of surrounding skin
- General (Ease of use, Dressing retention, durability, patient comfort & convenience)
- Pain on application of dressing
- Pain on removal of dressing
- Overall performance of dressing
- Use of post operative oral antibiotics

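### Section 7 limits formal adverse event reporting to events judged related to Avance Solo, so formally reported adverse events are not comparable between the arms

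*Combined protocol and SAP*

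**What the plan says.** The study is described in Section 2.1 as "Open label, two armed, prospective, single center, quality equivalency assessment", with 30 patients per arm (Section 4.1) and computer-generated randomisation (Section 8).

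Section 7 argues that the product is already marketed and is used within its indications under normal practice. It concludes that "only adverse events that are related to the evaluation product are to be reported". The next paragraph covers device deficiencies, adverse device effects and serious adverse device effects "that are considered as being related to the use of the medical device Avance Solo is reported". A product-related adverse event is then defined as one "possibly, probably or highly probably caused by the use of the evaluation product", to be entered on a form and sent to the manufacturer of Avance Solo. The same section also requires the IRB to be informed of any adverse event, under that board's own policies.

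Section 3.3 returns unused evaluation products to the manufacturer and then says: "The control product will be managed by the Mount Sinai West operating room product acquisition supply system".

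Among the reasons for withdrawal, the end-of-evaluation list in Section 6.1 offers "product related adverse event, lack of response, poor compliance".

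**The concern.** In a randomised comparison, a harm count can be compared between arms only if both arms are asked the same question over the same period. Section 7 appears to ask it of one arm only, and only after a clinician who knows the allocation has decided that the device was at least possibly the cause. The reasoning given for the rule suits vigilance on a single marketed product. It does not suit a two-arm study whose objectives (Section 1.2) include an overall comparison of the two dressings.

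Three things are at stake. First, a table of formally reported events would carry an imbalance created by the rule, and it would run against Avance Solo. Second, because events judged unrelated are not reported in either arm, attribution could not be re-examined later. Third, Section 8 presents the study as a pilot to test assumptions for a larger trial, and one-sided counts cannot supply its comparative safety assumptions.

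**Working it through.** **Step 1. Which product does the rule mean?** The plan gives no formal definition, so the texts have to be weighed.

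| Points to Avance Solo only | Points to both dressings, or is neutral |
|---|---|
| Section 7 names Avance Solo in the device-event clause | The Section 3 heading uses an optional plural, and the control dressing is item 3.2 beneath it |
| The adverse event form goes to the Avance Solo manufacturer; the control is another company's product (Section 3.2) | The dressing-removal list in Section 6.1 mentions product-related adverse events, if required, without naming an arm |
| Section 3.3 separates evaluation products from the control product | Section 7 requires IRB notification of any adverse event |

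The left column is the more specific. The Section 6.1 item takes its meaning from the Section 7 definition, which refers back to the evaluation product. IRB notification is a duty to the board and does not set up a study dataset. Avance-only is therefore the best reading, but it is an inference, and the text is inconsistent.

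**Step 2. What is still collected in both arms?** The following have no arm restriction and no causality filter:
- infection, dehiscence, delayed healing and drainage, at Days 21, 42 and 90 (Section 5.2);
- skin necrosis, cellulitis, abscess and haematoma over the same period (Sections 1.2 and 5.2), with seroma and periwound oedema in Section 1.2;
- damage to the wound and surrounding skin, skin condition, pain and comfort at dressing removal (Section 6.1);
- antibiotic use and readmission (Section 6.1), and length of stay (Section 8).

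**Step 3. What is left out?** Events judged unrelated are not reported in either arm. The outcome lists have no item for death, reoperation, systemic events, or falls and tubing injuries, although Section 5.3 warns of trip, pressure and tourniquet hazards. The listed skin-damage items grade severity but do not ask about relatedness, seriousness or outcome. For a control patient, the product-related withdrawal reason has no clear meaning under the Section 7 definition.

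**Step 4. Illustration of size.** The plan states no adverse event rate, so there is no figure to reproduce. Assume the same true rate q of product-related events in both arms, every Avance Solo event reported, and no control event reported.

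- Expected events per arm: 30q, which is 3 at 10% and 6 at 20%.
- Chance of at least one true control event: 1 − (1 − q)^30, which is 96% at 10% and 99.9% at 20%. The recorded count would still be 0.
- Two-sided Fisher p for x/30 v 0/30: 2 × C(30, x) / C(60, x).

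| Recorded | Fisher p |
|---|---|
| 3/30 v 0/30 | 2 × 4,060 / 34,220 = 0.237 |
| 4/30 v 0/30 | 0.112 |
| 5/30 v 0/30 | 0.052 |
| 6/30 v 0/30 | 2 × 593,775 / 50,063,860 = 0.024 |

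Six or more Avance Solo events are needed to pass 0.05. The binomial chance of that is 7% at q = 10% and 57% at q = 20%.

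A genuine 0/30 would give a one-sided 95% upper limit of 1 − 0.05^(1/30) = 9.5%. A zero produced by the reporting rule gives no such bound.

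**The case against.** The strongest reply is that most local harm is already captured. A skin reaction under the control dressing would be graded at removal, and wound complications are assessed in both arms to Day 90 whatever their cause. This stands. A reader might infer from Section 7 that control-arm harms are zero by rule, that a control-dressing reaction goes unrecorded, or that the arms cannot be compared for safety at all. The documents do not support any of these. The zero would apply only to the formal adverse event stream, and Sections 1.2, 5.2, 6.1 and 8 provide a two-arm comparison of wound and dressing outcomes.

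It can also be said that exclusion of the control is never stated outright. The device-event clause reads like inserted agreement text serving the manufacturer's own vigilance, and it refers to an Exhibit A that is not in the text available for review. This stands as a limit on certainty. It does not remove the opening rule of Section 7, which is part of the protocol's own reasoning and restricts reporting whichever product is meant.

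Finally, the event rates above are assumed, Section 8 plans a single chi-squared test on wound complication and calls the data exploratory, and only the top of the assumed range passes 0.05. All of that is correct. The p-values show how a one-sided count could mislead, not what the trial will report.

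**Conclusion.** The point holds in a limited form. On the best reading of Section 7, formal adverse event reporting covers only events that an unmasked clinician links to Avance Solo. Formally reported adverse events and the product-related withdrawal reason are then not comparable between arms. Comparative safety statements have to rest on the wound and dressing outcomes collected in both arms, which are imprecise at 30 per arm.

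The size depends on a rate the plan does not give. At assumed equal true rates of 10% to 20%, the recorded imbalance would be about 3 to 6 events against none. The primary wound complication comparison is unaffected. If the evaluation product was meant to include the control dressing, the one-sidedness disappears. The open-label causality filter and the loss of events judged unrelated remain. The matter deserves correction before enrolment but does not undermine the study's main aim.

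**What to change.** In Section 7:
- Define *evaluation product*, say whether it includes the control dressing, and reconcile the related-only rule with the sentence on informing the IRB of any adverse event.
- Record adverse events in both arms on the same form, through the Day 90 visit, regardless of attribution. Include events that the wound and dressing items do not already cover.
- Make relatedness to the assigned dressing a separate field, and use the same definition for the withdrawal reason in Section 6.1.
- Tabulate by randomised arm, for all events and for those judged related.
- Keep Avance-only reporting to the manufacturer as a separate duty.

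The cost is revised wording and slightly more data entry at visits already planned in Section 5.2. The current form is designed to go to one manufacturer and was not available for review, so it may need adapting for control patients.

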#### 8 STATISTICAL CONSIDERATIONS

A Chi squared evaluation of the data will be carried out in regard to the dichotomous yes/ no variable of post operative wound complication of not. The two groups will be randomized based upon a computer generated randomization schedule. Due to the small numbers the randomization will not be controlled for the surgical type.

Based upon the current literature the expected wound complication rate of the associated wound complication rate would be 16% (or 5/30), based upon best treatment effect of NPWTi the rate of wound complication would be 8% or (2/30). While this is a clinically significant and cost significant difference, in order to show a statistically significant difference at these levels, with an P $\beta$  of 0.8 and a P $\alpha$  of 0.05, the study would have to enroll a cohort of 324 patient with 162 patients in each. To date no study of post operative wound dressings has approached this level of statistical validity. Prior to embarking on any such study, a pilot study such as this needs to be undertaken to validate the basic assumptions.

Cost analysis of post operative wound complications will not be collected as a portion of this data, although LOS and freedom from readmission will be assessed. The data set is seen as exploratory and is not powered to find statistical significance.

#### 9 ADDITIONAL INFORMATION

#### 9.1 RECORD KEEPING

# 9.1.1 Questionnaires

The questionnaires provided created by the investigator team, and will be used to document all findings related to the evaluation. Please complete all questions legibly in ink. Where possible please write any text in English.

# 9.1.2 Evaluation File

The evaluation file provided by the information technology services at Mount Sinai healthcare system, it is a fire wall protected HIPPA. Evaluation files will not be kept on personal computers, thumb drives and will only be used on hospital based IT supported systems.

#### 9.2 EVALUATION PROGRESS UPDATES

This sponsor can ask for appropriate progress updates during the course of the evaluation

#### 9.3 USE OF EVALUATION FINDINGS

The investigator will not use the results of this evaluation without the written consent of the Mölnlycke, for the purposes of this document e-mail communication is equivalent to written consent.

The goal of the evaluation will be a minimum of an abstract submission at a mutually agreed upon national and/or international meeting.

Secondary goal of the evaluation will be to provide a nidus for publication in and national or international journal.

#### 10 ETHICAL AND LEGAL ISSUES

#### 10.1 DECLARATION OF HELSINKI

The evaluation will be performed in accordance with the guidelines of the Declaration of Helsinki (1964) and subsequent revisions. A copy of the current Declaration of Helsinki will be provided if requested by the evaluation Clinician.

# 10.2 CONFIDENTIALITY

The patient will be identified throughout the evaluation and documentation by the number allocated to them during the evaluation. The sponsor will therefore not receive any information that could be used to identify patients participating in the evaluation.

#### 10.3 INSURANCE

Product Liability Insurance has been purchased by Mölnlycke.

# 10.4 PATIENT CONSENT

Patients will be screened by the PI, study investigators, and coordinators through a medical record review in order to identify potentially eligible patients. Study personnel conducting a medical record review for potential subjects will look for elements of PHI that will help research personnel determine eligibility (based on the inclusion and exclusion criteria listed earlier) and enable them to inform study physicians of eligible participants. These identifiers include the following: Names, all geographic subdivisions smaller than a state, all elements of dates (except year) for

dates directly related to an individual, telephone numbers, social security numbers, medical records numbers, photographic images and videos of the study wound (these images will not contain identifiers). Only these identifiers will be shared with the study physicians via email from research personnel to determine if it is appropriate to approach the patient about the study. These candidates will be identified by study investigators.

Before being admitted to the clinical evaluation, the patient must have consented to the collection of their data during their participation in the evaluation, after the nature, scope and possible consequences of the evaluation have been explained in an understandable form. Candidates will be consented in a private setting and their information will be kept confidential, as only de-identified information will be collected from their for the purpose of the study. Subjects will consent to the indefinite retention of their de-identified data.

Although a specific consent form is not being provided for this evaluation, the questionnaires contain a space for the evaluation Clinician to sign to confirm that they have explained the evaluation to the patient and that the patient has agreed to take part.

For markets or centres where ethics or IRB approval is not required consent will still be required. Where ethics or IRB is required an approved consent form will be used.

The Clinician will not undertake any measures relating to the evaluation until consent has been obtained.

After consent is obtained, data will be collected from the EMR, study specific procedures, and the patient to complete screening, follow-up and final visit documentation, as well as the patient satisfaction questionnaire.

